5.3. OTHER ENDPOINTS

None

5.4. COVARIATES

Demographic and clinical characteristics are collected during the baseline period, at the index date or during follow-up period.

Variable	Role	Data source(s)	Operational definition
Sex Category	Baseline characteristic	Index date	Dichotomous variable equals 1 if sex is male and 2 if female
Age	Baseline characteristic	Index date	Age (in years) at the index date
Age (> 80y, >90 y)	Sub-group identifier	Index date	Age (in years) at the index date
Body weight	Baseline characteristic	Baseline period	\geq 60 kg or < 60 kg
eGFR (continuous)	Baseline characteristic	Baseline period	Value in the baseline If a patient has multiple eGFR values, the values closest to the index date will be adopted If a patient does not have eGFR values, but has serum creatinine values, an eGFR value is

Variable	Role	Data source(s)	Operational definition
			calculated from a serum creatinine value using fomulas.
eGFR (categorical)	Baseline characteristic	Baseline period	\geq 50 ml/min or < 50 ml/min If a patient does not have eGFR values, but has serum creatinine values, an eGFR value is calculated from a serum creatinine value using fomulas.
Serum creatinine (continuous)	Baseline characteristic	Baseline period	Value in the baseline If a patient has multiple eGFR values, the values closest to the index date will be adopted If a patient does not have serum creatinine values but has eGFR values, a serum creatinine value is calculated from eGFR value using fomulas
Serum creatinine (categorical)	Baseline characteristic	Baseline period	\geq 1.5mg/mL or < 1.5 mg/mL If a patient does not have serum creatinine values but has eGFR values, a serum creatinine value is calculated from eGFR value using fomulas
CHADS2	Baseline characteristic	Baseline period	CHADS2 score will be calculated based on age and the presence of congestive heart failure, hypertension, diabetes, and stroke or TIA.
CHA2DS2-VASc	Baseline characteristic	Baseline period	Score calculated by appointing 1 point each for congestive heart failure/left ventricle dysfunction, hypertension, diabetes, vascular disease (prior MI, peripheral arterial disease, or aortic plaque), age between 65-74, female gender; and 2 points each for age >75 years and prior stroke, TIA, or
Heart failure diagnosis	Baseline characteristic	Baseline period	thromboembolism. Dichotomous variable equals 1 if there are ≥1 diagnoses for heart failure ICD-10 or disease codes during the baseline period.
Coronary heart disease diagnosis	Baseline characteristic	Baseline period	Dichotomous variable equals 1 if there are ≥ 1 diagnoses for coronary heart disease ICD-10 or disease codes during the baseline period.
Peripheral arterial disorder diagnosis	Baseline characteristic	Baseline period	Dichotomous variable equals 1 if there are ≥1 diagnoses for peripheral arterial disorder ICD-10 or disease codes during the baseline period.
Myocardial infarction diagnosis	Baseline characteristic	Baseline period	Dichotomous variable equals 1 if there are ≥1 diagnoses for myocardial infarction ICD-10 or disease codes during the baseline period.
Hyperthyroidism or thyrotoxicosis	Baseline characteristic	Baseline period	Dichotomous variable equals 1 if there are ≥1 diagnoses for hyperthyroidism ICD-10 or disease codes during the baseline period.
Stroke, TIA or SE diagnosis	Baseline characteristic	Baseline period	Dichotomous variable equals 1 if there are ≥1 diagnoses for Stroke, TIA or systemic embolism ICD-10 or disease codes during the baseline period.
Renal dysfunction diagnosis	Sub-group identifier	Baseline period	Dichotomous variable equals 1 if there are ≥1 diagnoses for renal dysfunction ICD-10 or disease codes during the baseline period.
Liver dysfunction diagnosis	Baseline characteristic Sub-group identifier	Baseline period	Dichotomous variable equals 1 if there are ≥1 diagnoses for liver dysfunction ICD-10 or disease codes during the baseline period.
Bleeding diagnosis	Baseline characteristic	Baseline period	Dichotomous variable equals 1 if there are ≥1 diagnoses for bleeding ICD-10 or disease codes during the baseline period.

Variable	Role	Data source(s)	Operational definition
Hypertension diagnosis	Baseline characteristic Sub-group identifier	Baseline period	Dichotomous variable equals 1 if there are ≥1 diagnoses for hypertension ICD-10 or disease codes during the baseline period.
Refractory hypertension diagnosis	Sub-group identifier	Baseline period	Dichotomous variable equals 1 if there are prescriptions of ATC codes or receipt codes for all of the following 4 drugs during the baseline period; calcium channel blocker, ACE inhibitor/ARB, thiazide diuretics and MR antagonist/a-blocker/b- blocker
Diabetes mellitus diagnosis	Baseline characteristic Sub-group identifier	Baseline period	Dichotomous variable equals 1 if there are ≥ 1 diagnoses for diabetes mellitus ICD-10 or disease codes during the baseline period.
Cancer diagnosis	Baseline characteristic Sub-group identifier	Baseline period	Dichotomous variable equals 1 if there are ≥1 diagnoses for diabetes mellitus ICD-10 or disease codes during the baseline period.
Treated with antiplatelet drug	Baseline characteristic	Baseline period	Dichotomous variable equals 1 if there are ≥1 prescriptions of antiplatelet drug ATC or receipt codes during the baseline period.
Treated with antiplatelet drug (>28 d)	Sub-group identifier	Baseline period	Dichotomous variable equals 1 if there are ≥1 prescriptions of antiplatelet drug ATC or receipt codes during the baseline period.
Treated with NSAIDs	Baseline characteristic	Baseline period	Dichotomous variable equals 1 if there are ≥1 prescriptions of NSAIDs ATC or receipt codes during the baseline period.
Treated with NSAIDs (>90 d)	Sub-group identifier	Baseline period	Dichotomous variable equals 1 if there are ≥1 prescriptions of NSAIDs ATC or receipt codes during the baseline period.
Treated with gastric secretion inhibitor	Baseline characteristic	Baseline period	Dichotomous variable equals 1 if there are ≥ 1 prescriptions of gastric secretion inhibitor drug ATC or receipt codes during the baseline period.
Treated with statin- based drug	Baseline characteristic	Baseline period	Dichotomous variable equals 1 if there are ≥1 prescriptions of statin-based drug ATC or receipt codes during the baseline period.
Treated with anti- hypertensives	Baseline characteristic	Baseline period	Dichotomous variable equals 1 if there are ≥1 prescriptions of anti-hypertensive ATC or receipt codes during the baseline period.
Treated with anti- arrhythmics	Baseline characteristic	Baseline period	Dichotomous variable equals 1 if there are ≥1 prescriptions of anti-arrythmics ATC or receipt codes during the baseline period.
Treated with beta- blockers	Baseline characteristic	Baseline period	Dichotomous variable equals 1 if there are ≥ 1 prescriptions of beta-blockers ATC or receipt codes during the baseline period.
Treated with heparins	Baseline characteristic	Baseline period	Dichotomous variable equals 1 if there are ≥ 1 prescriptions of heparins ATC or receipt codes during the baseline period.
Cardioversion	Baseline characteristic	Baseline period	Dichotomous variable equals 1 if there is ≥1 operation of cardioversion receipt codes during the baseline period.
Alcohol abuse	Sub-group identifier	Baseline period	Dichotomous variable equals 1 if there are ≥1 diagnoses for Alcohol abuse ICD-10 or disease codes during the baseline period.
Bleeding diagnosis	Sub-group identifier	Baseline period	Dichotomous variable equals 1 if there are ≥1 diagnoses for major or any bleeding ICD-10 or disease codes during the baseline period

Variable	Role	Data source(s)	Operational definition	
Peptic ulcer diagnosis	Sub-group identifier	Baseline period	Dichotomous variable equals 1 if there are ≥1 diagnoses for peptic ulcer ICD-10 or disease codes during the baseline period	
Hemorrhagic stroke diagnosis	Sub-group identifier	Baseline period	Dichotomous variable equals 1 if there are ≥1 diagnoses for hemorrhagic stroke ICD-10 or disease codes during the baseline period	
Low body weight (<40 kg)	Sub-group identifier	Baseline period	Body weight during baseline period	
Polypharmacy	Sub-group identifier	Baseline period	Dichotomous variable equals 1 if there are ≥ 6 prescriptions of oral drug ATC or receipt codes during the baseline period.	
PT-INR (Prothrombin time- international normalized ratio)	potential confounder	Baseline period	Continuous variable. * Only available for patients treated with warfarin	
Physician specialty	potential confounder	Index date	Dichotomous variable equals 1 if a physician specialty on the index date is categorized into a cardiac specialty and 0 if others. Following specialties will be categorized as the cardiac specialty: cardiology stroke, cardiovascular surgery, pediatric cardiology, neurosurgery, cardiovascular medicine, and neurology. If there are ≥ 1 specialties but including the cardiac specialty, the physician specialty will be regarded as the cardiac specialty.	
Hospital size (<500 beds or not)	potential confounder	Index date	Dichotomous variable equals 1 if hospital size on the index date is <500 beds and 0 if ≥500 beds.	
Hospitalization status on index date	potential confounder	Index date	Dichotomous variable equals 1 if hospitalization status is inpatient and 0 if outpatient.	
INR (warfarin cohort)	Baseline characteristic	Baseline period	Continuous variable. * Only available for patients treated with warfarin	
Apixaban dose (2.5 g BID)	Baseline characteristic	Baseline period	2.5 mg BID or 5mg BID * Only available for patients treated with apixaban	

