7. STATISTICAL METHODOLOGY AND STATISTICAL ANALYSES

7.1. STATISTICAL METHODS

7.1.1. Calculation of Propensity Score

In this study, balanced cohorts (apixaban vs. warfarin) will be created by an IPTW method. Propensity scores will be estimated by unconditional logistic regression analyses that incorporate potential predictors of therapy as independent variables in the regression and cohort status as the outcome. Using calculated propensity score an IPTW method will be applied to balance the warfarin and apixaban cohorts, which will be used for the comparisons of all endpoints (sections 5.1 and 5.2). The following covariates will be included in the logistic regression for calculation of propensity score:

• age on index date

- gender
- CHADS2 score in baseline
- CHA2DS2-VASc score in baseline
- heart failure diagnosis in baseline
- coronary heart disease diagnosis in baseline
- peripheral arterial disorder diagnosis in baseline
- myocardial infarction diagnosis in baseline
- hyperthyroidism or thyrotoxicosis in baseline
- TIA diagnosis in baseline
- stroke or SE diagnosis in baseline
- renal dysfunction diagnosis in baseline
- liver dysfunction diagnosis in baseline
- bleeding diagnosis in baseline
- hypertension diagnosis in baseline
- diabetes mellitus diagnosis in baseline
- treated with antiplatelet drug in baseline
- treated with NSAIDs in baseline
- treated with gastric secretion inhibitor in baseline
- treated with statin-based drug in baseline
- treated with anti-hypertensives in baseline
- treated with anti-arrhythmics in baseline
- treated with beta-blockers in baseline
- treated with heparins in baseline
- cardioversion in baseline

The operational definitions for the above covariates are shown in the Section 5.4.

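### As written in SAP 5.4, the CHA2DS2-VASc rule gives a patient aged exactly 75 no age points; the effect is small and the correction is one character

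*SAP*

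**What the plan says.** The covariate table in SAP 5.4 gives the operational definition of the score. Its one-point items include "age between 65-74, female gender". Its two-point items begin with "2 points each for age >75 years", followed by prior stroke, TIA or thromboembolism. Age itself is defined in the same table as "Age (in years) at the index date".

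SAP 7.1.1 lists "CHA2DS2-VASc score in baseline" among the covariates of the logistic propensity model, with "age on index date" as a separate covariate. It then says: "The operational definitions for the above covariates are shown in the Section 5.4". The score also has the role of a baseline characteristic in 5.4. Protocol 9.3 lists the score without a scoring rule and leaves detailed definitions to the SAP.

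The same SAP table has a categorical serum creatinine entry, whose two categories are at or above "1.5mg/mL or < 1.5 mg/mL".

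**The concern.** The two age bands do not meet. A score meant to rise with age falls at 75 and then rises again, which cannot be intended. Because 7.1.1 names Section 5.4 as the source of definitions, this is the text a programmer would follow.

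The score is used in three places:
- as a covariate in the propensity model (7.1.1);
- in the baseline comparison before and after weighting (7.1.3 and 7.1.4), from which readers judge the stroke risk of the cohort;
- in the 10% standardized-difference check (7.1.2), which decides under 7.1.6 whether a variable is added to the Cox model.

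The separate age term limits what the error can do to the weights. It does nothing for the reported score distribution.

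**Working it through.** The plan states no figure that depends on this rule, so there is none to reproduce.

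**Inputs from SAP 5.4.** 1 point if 65 ≤ age ≤ 74; 2 points if age > 75; age in years at the index date.

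**Step 1: the rule by age.** Age points as printed, and with the upper band starting at 75:

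| Age | As printed | With ≥75 |
|---|---|---|
| 64 | 0 | 0 |
| 65 | 1 | 1 |
| 74 | 1 | 1 |
| 75 | 0 | 2 |
| 76 | 2 | 2 |
| 80 | 2 | 2 |

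Over every whole age from 18 to 110, the two versions differ only at 75. If age were held as a fraction of years, the printed rule would leave uncovered everything above 74 up to and including 75.

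**Step 2: does another section settle it?** The CHADS2 entry in 5.4 uses age but gives no cut-off. The power tables in 7.1.9 print an inclusive ≥ 75 years, but as a subgroup label from an earlier trial and not as a scoring rule. The protocol gives no rule. Nothing assigns points at age 75.

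**Step 3: size in the baseline table.** Understatement of the mean score = share aged 75 × points lost. The share is not in the documents; 1% to 5% is an assumption.

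- If 75 belongs in the 2-point band: 0.01 × 2 = 0.02, up to 0.05 × 2 = 0.10.
- If 75 belonged in the 1-point band: 0.01 × 1 = 0.01, up to 0.05 × 1 = 0.05.

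SAP 7.1.9 reports more than 10,000 eligible patients on each drug. For an assumed total of 20,000, the number affected is 20,000 × 0.01 = 200 to 20,000 × 0.05 = 1,000.

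**Step 4: size in the balance check.** Assume that the share aged 75 differs between cohorts by 0.5 to 1 percentage point and that the score has a standard deviation of 1.5 (neither figure is in the documents). The standardized difference then moves by 2 × 0.005 / 1.5 = 0.007 to 2 × 0.01 / 1.5 = 0.013, against the plan's limit of 0.10.

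**Step 5: the creatinine unit.** Since 1 dL = 100 mL, 1.5 mg/mL is 150 mg/dL. If values are stored in mg/dL and compared with the bare number 1.5, patients split at 1.5 mg/dL. If values are first converted to the printed mg/mL, essentially all fall below the cut-off. The documents do not say in which unit the database stores creatinine. Creatinine is not in the 7.1.1 covariate list, which uses a renal dysfunction diagnosis.

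**The case against.** The best reply is that this is a mistyped inequality with almost no consequence. The documents show a printed rule, not analysis code, and a programmer who knows the score may have used ≥75 anyway. That is fair: what is shown is that the definition as printed gives a wrong value, not that any patient has been misclassified.

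A sign lost in extracting the PDF text is also possible. The cell is visibly broken, with its last word displaced into the heart failure row. Against that, the ≥ sign survives many times in the same table and again in 7.1.9, so the loss is unlikely. A look at the source page would settle it.

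A reader might infer that the weights, and hence the hazard ratio, are materially biased. The documents do not support that. Age, gender, heart failure, hypertension, diabetes, stroke or SE, TIA, myocardial infarction and peripheral arterial disorder all enter the propensity model separately, so the score is largely redundant there, and both cohorts are scored by the same rule.

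A reader might also infer that the creatinine cut-off puts every patient in the lower category. That requires a conversion to mg/mL that no section describes, and a stored unit that no section states.

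**Conclusion.** The point holds as a defect in a stated definition. SAP 5.4 gives no age points at exactly 75, nothing else in the documents repairs it, and the affected score is both a propensity covariate and a reported baseline characteristic.

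Its importance is low. The mean score would be too low by roughly 0.02 to 0.10, which rests on the assumed 1% to 5% share and on age 75 belonging in the 2-point band. The internal gap proves that one of the bands must be extended. The choice of the upper band is the natural reading but is not stated in the documents. No endpoint, test or sample-size figure depends on the score.

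The creatinine entry is a query only: whether the printed unit matches the stored one. It bears on a descriptive baseline category.

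**What to change.** In SAP 5.4, change the upper age band of CHA2DS2-VASc from >75 to ≥75 years and say that age is in completed years, so that the two bands meet. The CHADS2 age cut-off could be stated in the same edit. Check that the program uses the corrected bands; if it already does, only the text changes. If it does not, the score, the propensity model, the weights and the analyses that use them need to be rerun.

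Confirm the unit in which the database stores serum creatinine and make the printed unit agree with it.

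The cost is a few words in one table and a short code check. Endpoints, sample size and data extraction are unaffected.

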First, all patients with NVAF who are newly diagnosed and initiated apixaban or warfarin will be extracted from the database. Among these patients, patients with at least one predetermined high bleeding risks will be extracted. In this study, predetermined high bleeding risks are 1) patients with hypertension diagnosis, 2) patients with liver dysfunction, 3) patients with renal dysfunction diagnosis, 4) patients with a history of bleeding, 5) patients with hemorrhagic stroke, 6) patients with alcohol abuse, 7) patients with concomitant used of antiplatelet drugs, 8) patients with chronic (continuously for longer than 90 days) concomitant use of Non-steroidal antiinflammatory drug (NSAID), 9) highly elderly (> 80 years old), 10) patients with refractory hypertension, 11) patients with a history of peptic ulcer diagnosis, 12) patients with active cancer, 13) patients with diabetes mellitus, 14) patients whose body weight is <40kg, 15) patients with polypharmacy (sea Section 5.4 for the definition). Patients with at least one predetermined high bleeding risk factor will be divided into two cohorts, apixaban and warfarin cohorts, based on the first prescribed drug just after the NVAF diagnosis. Patient characteristics will be balanced by using an inverse probability of treatment weighting (IPTW) method to create balanced apixaban and balanced warfarin cohorts. Comparisons will be conducted by using these balanced warfarin and apixaban cohorts (Kaplan-meier curves, incidence rates per 1,000 person-year and hazard ratio with 95% confident intervals). The primary safety and effectiveness analyses are comparison of apixaban with warfarin in patients with at least one predetermined risk factor for bleeding.

- Second, after the first analysis, we will conduct separate interaction analysis of the treatment (apixaban vs. warfarin) and one of the 15 risk factors (e.g., hypertension yes vs no, etc) to see if treatment effects are consistent among patients with or without each specific factor
- Third, patients will be stratified by risk factors into 15 subgroups, and same IPTW analyses as described in the step 1 will be conducted only in the subgroups with adequate sample sizes.

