4.1.1. Inclusion criteria

Patients must meet all of the following inclusion criteria to be eligible for inclusion in the study:

- 1. Patients with diagnosis with NVAF anytime in the baseline period or on the index date,
- 2. The first prescribed anticoagulant is apixaban or warfarin after the index date.
- 3. No use of the any oral anticoagulants (OACs) during the baseline period (the 180 days before the index date)
- 4. Age of 18 years or older on the index date.

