4.4. SUBGROUPS

Following subgroups will be created and exploratory analyses for primary endpoints (major bleeding or stroke/SE) will be performed.

Variable	categories
Hypertension diagnosis	Yes or No
Liver dysfunction diagnosis	Yes or No
Renal impairment diagnosis	Yes or No
Bleeding diagnosis including intracranial hemorrhage	Yes or No
Treated with antiplatelet drug (>28d)	Yes or No
A go	>80 years
Age	>90years
Peptic ulcer diagnosis	Yes or No
Cancer diagnosis	Yes or No
Low body weight	<40 kg
Diabetes mellitus diagnosis	Yes or No
Polypharmacy	≥ 6 concomitant drugs

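### Drug use that the SAP names as concomitant is flagged from prescriptions in the 180 days before the oral anticoagulant starts, with no overlap required

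*SAP*

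**What the plan says.** SAP 2.1 lists 15 bleeding-risk factors. Two of them are named as concomitant use: "7) patients with concomitant used of antiplatelet drugs" and "8) patients with chronic (continuously for longer than 90 days) concomitant use of Non-steroidal antiinflammatory drug (NSAID". A third is polypharmacy, which 2.1 refers to section 5.4 and which the subgroup table in 4.4 describes as "≥ 6 concomitant drugs". SAP 2.2.4 and the analysis tables in 7.2.3 again describe the antiplatelet subgroup as concomitant use.

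The derivations are in SAP 5.4:

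- **Antiplatelets:** "Dichotomous variable equals 1 if there are ≥1 prescriptions of antiplatelet drug ATC or receipt codes during the baseline period". The same sentence serves both the covariate and the subgroup identifier labelled >28 d.
- **NSAIDs:** "Dichotomous variable equals 1 if there are ≥1 prescriptions of NSAIDs ATC or receipt codes during the baseline period". The same sentence serves both the covariate and the identifier labelled >90 d.
- **Polypharmacy:** six or more oral-drug prescriptions in the baseline period.

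Inclusion criterion 3 in SAP 4.1.1 fixes the window and what may happen in it: "No use of the any oral anticoagulants (OACs) during the baseline period (the 180 days before the index date". SAP 4.1.3.2 makes the index date the day apixaban or warfarin starts, and 4.1.3.1 starts follow-up the day after.

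**The concern.** The name of the factor and its definition describe different things. Concomitant use with an OAC can exist only from the index date onward, but the window that is searched ends before the first OAC prescription. The flag therefore records prior use, which may or may not have continued.

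The flags have three uses under SAP 2.1. A single factor is enough to admit a patient to the primary population. Each factor is crossed with treatment in an interaction analysis. Antiplatelet use and polypharmacy are also candidate subgroups with their own weighted comparison. A reader of the antiplatelet subgroup result will take it as evidence on an OAC combined with an antiplatelet, and the flag does not establish that combination.

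**Working it through.** The plan states no figure on this point, so the check compares definitions and timing.

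**1. Does the window include the index date?** No. The baseline period is the 180 days before index. SAP 4.1.1, criterion 1, names the index date as an alternative to the baseline period, and the data-source columns in SAP 5.4 and Protocol 9.3 keep the two apart. All three drug-use factors have the baseline period as their source.

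**2. Does any rule require overlap?** No row asks for a prescription on or after index, or for supply that reaches index. The opening sentence of SAP 5.4 allows collection at index or during follow-up, but these rows do not use that option. Appendix 10.3.6 only refers back to 5.4.

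**3. Which patients are flagged?** Days are counted from index = day 0.

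| Patient | Record | Flag in 5.4 | Supply at index |
|---|---|---|---|
| A | One antiplatelet prescription at about day −150 (5 × 30), assumed 28 days' supply, none later | 1 | No |
| B | Antiplatelet supply runs through day 0 | 1 | Yes |
| C | Antiplatelet first prescribed after day 0 | 0 | No; combined use begins later |
| D | One oral drug refilled every 30 days (assumed): 180 / 30 = 6 prescriptions | Polypharmacy = 1 | At most one drug |

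A and B are scored alike. D can qualify because nothing in the row requires the six prescriptions to be for different drugs.

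**4. Is this just the missing duration rule?** No. The >28-day and >90-day limits appear in the labels and are absent from the definitions, which is a separate defect in the same rows. Restoring them would not settle the timing. A patient with 91 continuous days of NSAID starting on day −180 has supply to day −180 + 91 − 1 = −90. That exceeds 90 days and still ends 90 days before the OAC starts.

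**5. How many patients are affected?** This cannot be computed. The documents do not give the share of flagged patients without supply at index, or the number admitted to the primary cohort by one of these flags alone.

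**The case against.** The case for leaving the plan alone has several sound parts.

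- **Primary cohort.** Entry needs any one of 15 factors, among them hypertension, diabetes and age over 80. Only patients admitted solely through an out-of-date drug flag change the cohort, and they may be few. This stands.
- **Exploratory status.** SAP 3.2 and 7.1.7 draw no definitive conclusions from subgroups. Protocol section 8 drops the chronic-NSAID subgroup for size, and SAP 2.2.4 says it could be dropped. This lowers the stakes. The NSAID factor still counts for cohort entry and, under SAP 2.1, for interaction.
- **Meaning of the polypharmacy label.** Concomitant there may mean drugs taken together, not with the OAC, and SAP 2.2.4 speaks only of six or more medicines. That is a fair reading, but a count of prescriptions over 180 days does not show that the drugs were taken together either.
- **Open labelling.** SAP 4.4 and 5.4 call the antiplatelet subgroup treated with the drug for >28 d, and 5.4 states the baseline source. That is true, but 2.1, 2.2.4 and 7.2.3 call the same group concomitant users.
- **Limitations text.** Protocol 9.9 acknowledges claims-based misclassification of bleeding-risk factors in general. It does not mention this timing.

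A reader might also infer more than the documents support:

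- **That the baseline flags fail as propensity-score covariates.** They do not. Covariates measured before treatment choice are valid in that model. Stopping a drug because of the OAC chosen happens at or after that choice.
- **That past users carry no extra bleeding risk.** Nothing in the documents shows this, and former users may differ in underlying disease. The supportable statement is that past use is not the factor the SAP names.
- **That mixing past and current users biases a planned hazard ratio.** It could dilute the bleeding ratio of flagged to unflagged patients. The planned estimates compare apixaban with warfarin, and no bias in those has been shown.

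**Conclusion.** The mismatch is confirmed by the text. For antiplatelets and NSAIDs, the SAP names concomitant use and measures any prescription in an OAC-free window. For polypharmacy, it names six concomitant drugs and counts six prescriptions. No other section repairs this.

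What is affected is the meaning of the risk-factor flags: who may enter the cohort through them, what the interaction terms compare, and whom the antiplatelet and polypharmacy subgroups contain. The effect on the primary hazard ratios is unquantified and may be small. The conclusion rests on reading concomitant, for antiplatelets and NSAIDs, as use together with the study OAC. For polypharmacy it holds on either reading of the word. It also assumes that prescriptions are counted as section 5.4 is worded; a programmer might choose to count different drugs, but the text does not require it.

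**What to change.** In SAP 5.4, for the risk-factor and subgroup flags only:

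1. **Antiplatelets:** require days' supply that covers the index date, in addition to whatever duration rule is restored.
2. **NSAIDs:** require more than 90 continuous days of supply that reaches the index date.
3. **Polypharmacy:** count six or more distinct oral drugs with supply at the index date.
4. **Sensitivity analysis:** report results under the any-baseline-use definition.
5. **If days' supply is not available for these drugs:** rename the factors as baseline (prior) use in 2.1, 2.2.4, 4.4 and 7.2.3, and count distinct drugs for polypharmacy.

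Leave the baseline antiplatelet and NSAID covariates in the propensity model of SAP 7.1.1 unchanged.

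The cost is SAP wording and some programming. SAP 4.1.3.1 already uses days of supply for apixaban and warfarin, and the >28-day and >90-day labels presuppose duration data for antiplatelets and NSAIDs. Nothing confirms such data for all oral drugs, so availability must be checked first. The subgroups become somewhat smaller, and gaps in supply records will miss some true users.

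The change removes remote users and repeat refills of one drug. It does not detect a patient told to stop on the index date: with 28 days dispensed 10 days earlier, 28 − 10 = 18 days of recorded supply remain and the flag stays at 1. It also does not show use after index.
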